10.3. Data Transformation

For all continuous variables, mean, standard deviation, minimum, maximum, median, 25% quantile and 75% quantile will be calculated per treatment group and overall.

For all categorical variables counts and frequencies of categories will be calculated per treatment group and overall.

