10.3.5. Exploratory Analyses

10.3.5.1. %SPT area

For each patient the % SPT area (the area of SPT as a percentage of the total area of all TWs) will be calculated. From this a binary variable will be computed indicating whether % SPT area is $< 25\%$ or $\geq 25\%$. Cumulative and absolute frequencies for each category will be computed.

10.3.5.2. %TBSA

A binary variable indicating whether total %TBSA of all TWs is $\leq 15\%$ or $> 15\%$ will be calculated per patient. For this variable cumulative and absolute frequencies for each category will be computed.

10.3.5.3. *Application data*

For the patients of the NexoBrid and the gel vehicle arm the number of applications (0, 1, 2) will be determined. Cumulative and absolute frequencies will be computed for each category. Furthermore, for each patient the amount of NexoBrid gel each patient in the NexoBrid treatment arm has been exposed to, will be calculated.

10.3.5.4. *Maintenance of complete wound closure*

For each follow-up visit the information of complete wound closure for each TW will be aggregated to a binary variable indicating maintenance of complete wound closure on a patient level (i.e. complete wound closure for each TWs of a patient). Cumulative and absolute frequencies will be computed for each category.

10.3.5.5. *% wound area surgically excised for eschar removal*

% of wound area surgically excised for eschar removal, A_{total} , will be calculated using the following formula:

$$A_{total} = \frac{\sum_i (a_i * \%TBSA_i)}{\sum_i \%TBSA_i}$$

where $\%TBSA_i$ is the area of TW i (in % TBSA) and a_i denotes the % of wound area surgically excised for eschar removal of TW i.

10.3.5.6. *Incidence of reduction in interstitial/compartment pressure in circumferential extremities target wounds*

Interstitial/compartment pressure in circumferential extremities target wounds is measured within 1 hour (+30 min) prior to start of each eschar removal procedure and post-eschar removal. For each circumferential target wound and each eschar removal procedure a binary (yes/no) variable will be computed indicating whether reduction in interstitial/compartment pressure in that wound was present.

10.3.5.7. *POSAS*

The Patient Observer Scar Assessment Scale (POSAS) consists of two parts: a patient scale and an observer scale. Both scales contain six items that are scored numerically with 1-10. For each wound of a patient the total score of the patient scale will be computed as:

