1. The first analysis will be performed at the end of the Efficacy Assessment Period (EAP). This analysis will be the only inductive analysis of the trial and will include statistical tests for the primary and secondary endpoints as described below, as well for short-term safety endpoints (including time to wound closure). The analysis will be conducted, when 3 months had passed from the last patient reaching complete wound closure, in accordance with FDA guidance for industry *Chronic Cutaneous Ulcer and Burn Wounds — Developing Products for Treatment* “*Trial subjects generally should remain in the study for follow-up evaluation at least 3 months following complete wound closure. The purpose for this follow-up period is to help distinguish actual wound healing from transient wound coverage*”. At this time-point, data will be available for all patients on the primary end-point (proportion with complete eschar removal), the three secondary endpoints (proportion undergoing surgery, time to complete eschar removal, and blood loss) and short-term safety endpoints (including time to wound closure). Missing values for early drop outs etc. will be handled as described in Sections 10.1 and 10.2. The complete data set documented so far will be locked and analyzed as described above. In the analysis of adverse events and concomitant medication, for each patient only the data until the 3 months follow up will be analyzed in this stage. Data obtained after the 3 months follow up will be analyzed in the second and third stage of analysis. MVSS data, although captured in the eCRF for a few of the subjects at the stage of EAP, will not be included, revealed or analyzed during the EAP analyses.
2. The second analysis will be performed for the 12 months follow up period (STFU12) and will be started after the last patient has reached the 12m assessment. At this analysis, all accumulated safety data at the 12m follow-up will be analyzed, particularly the 12m MVSS assessment for cosmesis and function. The complete data set documented so far will be locked and analyzed as described below. In the analysis of adverse events for each patient only the data obtained after the 3 months follow up and until the 12 months follow up (including AEs and concomitant medications from the first stage that are ongoing) will be analyzed in this stage.

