11.1.2. Primary Efficacy variable

The primary efficacy variable will be analyzed using the FAS.

The proportions of patients who reached complete eschar removal at the end of the topical agent soaking period will be compared using logistic regression. The primary analysis will be based on the binary variable (yes/no): 'has complete eschar removal been achieved in all TWs' and will compare NexoBrid with the Gel Vehicle (for further definition and explanation of complete eschar removal see Section 1.1 of the protocol and Section 10.3.2 of this SAP). For handling of missing data see Section 10.1.1. The statistical test will be based on Fisher's exact test because of the small numbers expected in the Gel vehicle group. The odds ratio of achieving complete eschar removal for NexoBrid versus Gel Vehicle and its 95% confidence interval will be estimated using exact distribution methods and will be displayed as shown in Table 6. Bar plots will be shown for the proportions of patients who reached complete eschar removal.

If numerically possible, the comparison will supportively be adjusted for the stratification factor wound depth (all TWs full thickness, mixed TWs, all TWs deep partial thickness) by including

the factor in a logistic regression model together with the treatment variable (NexoBrid vs. Gel Vehicle). Similarly, if convergence of the estimation procedure can be obtained, then, in two other supportive analyses, the factor “Total %TBSA per patient” and the factor treatment center group (see Section 13.8.5 of the protocol as well as Section 11.1.7 of this SAP) will be included in a logistic regression model with the treatment variable. Statistical inference will be based upon exact distribution methods using the “exact” statement in the SAS procedure PROC LOGISTIC. The estimated regression coefficients of the regression analyses will be presented as displayed in Table 7.

The odds ratio of achieving complete eschar removal for NexoBrid versus Gel Vehicle will be estimated from these supportive models, as well as 95% confidence intervals and the level of statistical significance. The results will be displayed as shown in Table 6.

The primary efficacy analysis will be repeated on a wound level as an additional analysis using a mixed logistic regression model with a random effect for patient.

Furthermore, as an additional sensitivity analysis, the primary analysis will be repeated using the PP as analysis population.

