11.1.3. Secondary Efficacy variables

The secondary endpoints will be analyzed as described below and will compare efficacy in the NexoBrid group with the SOC group. Missing data will be handled by the methods described in Section 10.1. All secondary endpoints will be analyzed using the FAS. Sensitivity analyses will include analyzing the endpoints using the PP as analysis population.

11.1.3.1. *Incidence of surgical excision*

This is a binary yes/no variable and the proportion of patients who need excision for eschar removal will be compared using logistic regression. The explanatory variables in the model will include treatment, and the following variables: overall TW depth (all TWs full thickness, mixed TWs, all TWs deep partial thickness), “Total %TBSA per patient” and number of TWs (1, 2, ≥3). The odds ratio of requiring surgery for NexoBrid versus SOC will be estimated from the model, as well as 95% confidence intervals and the level of statistical significance. The results

will be displayed as shown in Table 6 and Table 7. Bar plots will be shown for the proportions of patients who needed excision for eschar removal.

If numerically possible, as a supportive analysis, the variable treatment center will be added into the logistic regression model and the analysis repeated.

As a sensitivity analysis, the logistic regression outlined above will be repeated using the PP as analysis population.

If any of the baseline factors, gender, age, percent SPT area (the area of SPT as a percentage of the total area of all TWs, classified as <25% or ≥25%), time from injury to randomization or number of TWs (1, 2, ≥3) are found to be significantly different between the treatment groups, then the factor will be included as an extra adjusting covariate in the logistic regression model described above as additional analysis.

As supportive analysis, the incidence of surgical excision for eschar removal will be compared between NexoBrid and Gel Vehicle using the same explanatory variables as in the main analysis of this endpoint.

A further supportive analysis will repeat the analysis (NexoBrid versus SOC) as described above, but on a wound level. I.e. a mixed logistic regression model with explanatory variables treatment, TW depth, %TBSA per wound and number of TWs and a random effect for patient will be performed.

11.1.3.2. *Time to complete eschar removal*

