ll = (censor=0)*log(g) + (censor=1)*log(G_t);
model time~general(ll);
RANDOM z ~ normal(0,sigma) subject=subject_id;
RUN;
```

where subject_ID is a unique identification number for each patient, time is the time to wound closure on a wound level. Censor is a censoring indicator, treatment_group gives the treatment group, spt gives the % area SPT (on a wound level), dpt gives the % area DPT (on a wound level), ft gives the % area FT (on a wound level), TBSA gives the %TBSA (on a wound level), number_tw2 is an indicator variable for the subject having 2 target wounds (patient level), number_tw3 is an indicator variable for the subject having ≥ 3 target wounds (patient level), center2,...,center5 are indicator variables for the individual being in center group 2,...,5 (patient level) and burn_data is a SAS data set containing the required information.

The SAS code presented above calculates the treatment effect in an accelerated failure time model with shared frailty assuming a log-logistic distribution of the data. The commonly used Weibull-distribution is not applicable in this case, because the AFT model is equivalent to a proportional hazards model.

The presented methods include information on all the target wounds of each patient and account for any within-patient correlation. Missing information due to incomplete follow-up is incorporated naturally into such analyses as censored observations.

Kaplan-Meier curves will be presented graphically (see Figure 3) and in a table (see Table 8) to display the distribution of time to complete wound closure under the two treatments.

If any of the baseline factors, gender, age, or percent SPT area (the area of SPT as a percentage of the total area of all TWs, classified as <25% or ≥25%) are found to be significantly different between the treatment groups, then the factor will be included as an extra adjusting covariate in a supportive analysis of time to complete wound closure.

Furthermore, time to reach 100% wound closure will be analyzed as outlined above as an additional analysis.

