11.1.4.12. Maintenance of complete wound closure

This is a binary (yes/no) variable (on a wound level). Maintenance of complete wound closure will be analyzed by displaying counts and percentages of wounds maintaining complete wound closure by treatment group (see Table 5). The proportion of wounds maintaining complete wound closure will be compared between treatment groups using a chi square test (or Fisher’s exact test in case of small estimated cell counts). Bar plots of the proportions of wounds maintaining complete wound closure will be shown.

The analysis will be conducted for the information present at month 1 and month 3 after wound closure.

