13.2. Lay-out and list of tables

For continuous variables, descriptive statistics will be presented as follows:

Table 4: Descriptive statistics of continuous variables per treatment.

Treatment	Variable								
	N	Missing	Mean	Std Dev	Min	Q1	Median	Q3	Max
NexoBrid									
SOC									
Gel Vehicle									
Total									

Table 5: Counts and (column) percentages of categorical variables per treatment.

Variable	Treatment								
	NexoBrid		SOC		Gel Vehicle		Total		
	N	(%)	N	(%)	N	(%)	N	(%)	
Category 1									
Category 2									
....									
Total									

Table 6: Confidence interval and test result for odds ratios

Comparison	Odds ratio	Test	p-value	Lower 95 % confidence bound	Upper 95 % confidence bound

Table 7: Presentation of test results and confidence intervals

	Estimate	Std Err	Test	Value of the test statistic	p-value	Lower 95 % confidence bound	Upper 95 % confidence bound
Variable							

Table 8: Table for Kaplan-Meier estimates per treatment

Time in days/hours	NexoBrid			SOC				
	Case	Censoring	At risk	%	Case	Censoring	At risk	%
0								
...								

Table 9: Counts and percentages of Medical History Conditions or Adverse Events by MedDRA System Organ Class.

System Organ Class	SOC		NexoBrid		Gel Vehicle		Total
	N	(%)	N	(%)	N	(%)	
Infections and infestations							
Neoplasms benign, malignant and unspecified (incl. cysts and polyps)							
Blood and lymphatic system disorders							
...							
Social Circumstances							
Total							

Table 10: Counts and percentages of Adverse Events by categories of a categorical variable

Variable	SOC	NexoBrid		Gel Vehicle		Total
		N	(%)	N	(%)	
Category 1						
Category 2						
Category 3						
...						
Total						

Table 11: Counts and percentages of concomitant medication with reference to ATC coding (1st stage analysis).

ATC code	Contents	Concomitant medication	Number of Patients	Indication				Pre-existing condition	Other	
				N	(%)	N	(%)	AE	N	(%)
A	Alimentary tract and metabolism									
B	Blood and blood forming organs									
C	Cardiovascular system									
D	Dermatologicals									
G	Genito-urinary system and sex hormones									
H	System hormonal preparations, excluding sex hormones and insulins									
J	Antimicrobials for systemic use									
L	Antineoplastic and immunomodulating agents									
M	Musculo-skeletal system									
N	Nervous system									
P	Antiparasitic products, insecticides and repellents									
R	Respiratory system									
S	Sensory organs									

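### Maintenance of wound closure is tested on pooled wounds as if a patient's wounds were independent, so the nominal 5% level of this supporting safety test is unreliable

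*SAP*

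**What the plan says.** - **The test (SAP 11.1.4.12).** Maintenance is a yes/no variable per wound. "The proportion of wounds maintaining complete wound closure will be compared between treatment groups using a chi square test", or Fisher's exact test when estimated cell counts are small, at months 1 and 3. No random effect, robust variance or other allowance for the patient is named.
- **The derived variable (SAP 10.3.5.4).** The wound information "will be aggregated to a binary variable indicating maintenance of complete wound closure on a patient level", meaning that every target wound of the patient is closed. Only frequencies are planned for it, and 10.3 adds that these are given by treatment group. Sections 11.1 to 11.3 contain no test of it.
- **Other wound-level analyses.** For time to wound closure, 11.1.4.1 says its methods "include information on all the target wounds of each patient and account for any within-patient correlation". The wound-level repeat of the primary analysis in 11.1.2 uses a "mixed logistic regression model with a random effect for patient". The wound-level repeat for surgical excision in 11.1.3.1 also has a random patient effect.
- **Role of the follow-up.** Section 11 quotes regulatory guidance on the three months after closure: "The purpose for this follow-up period is to help distinguish actual wound healing from transient wound coverage".

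**The concern.** The chi-square and Fisher tests treat each wound as an independent observation. Two wounds on one patient share that patient's age, comorbidity, care and compliance, so they probably tend to reopen or stay closed together. The pooled test then acts as if there were more information than the randomised patients supply, and the nominal 5% level can be exceeded.

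At stake is a statement about durability of closure. A chance imbalance in reopened wounds, perhaps driven by a few patients with several wounds, could be reported as a safety difference in either direction: apparent harm, or an unearned claim of more durable healing. This is the only comparison of maintained closure in the SAP that carries a p-value.

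**Working it through.** **Inputs from the SAP.** Two-sided 5% level (section 11); 75 NexoBrid, 75 SOC and 25 Gel Vehicle patients (9.3.1); one or more target wounds per patient (7.1), grouped as 1, 2 and 3 or more. The SAP states no rate, power or sample size for this variable, so the only plan figure to reproduce is the nominal 5%.

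**Assumptions (not in the SAP).** Wounds per patient 1/2/3 in proportions 33/33/33% (mix A, mean 2.0) or 50/30/20% (mix B, mean 1.7); ICC 0.1 to 0.6; maintenance 90% to 99%; switch to the exact test when an expected count is below 5.

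**Step 1, design effect.** With m wounds per patient, DE = 1 + (Σm²/Σm − 1) × ICC, and the true level is 2 × [1 − Φ(1.96/√DE)].

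- Mix A: Σm²/Σm = (1+4+9)/(1+2+3) = 2.333, so DE = 1 + 1.333 × ICC.
- Mix B: Σm²/Σm = (0.5+1.2+1.8)/(0.5+0.6+0.6) = 3.5/1.7 = 2.059, so DE = 1 + 1.059 × ICC.

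| ICC | Mix A: DE, level | Mix B: DE, level |
|---|---|---|
| 0 | 1.000, 5.0% | 1.000, 5.0% |
| 0.1 | 1.133, 6.6% | 1.106, 6.2% |
| 0.2 | 1.267, 8.2% | 1.212, 7.5% |
| 0.4 | 1.533, 11.3% | 1.424, 10.0% |
| 0.6 | 1.800, 14.4% | 1.635, 12.5% |

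With one wound per patient DE is 1 and the level is 5% at any ICC.

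**Step 2, simulation.** The formula ignores the discreteness that matters when reopening is rare. Beta-binomial wounds were therefore simulated with no true difference, 75 against 75 patients, 10,000 replicates per cell. Type I error of the pooled-wound test at ICC 0.2 / 0.4 / 0.6:

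| Maintenance | Mix A | Mix B |
|---|---|---|
| 90% | 7.5 / 11.5 / 14.7% | 7.3 / 9.3 / 12.3% |
| 95% | 7.5 / 10.8 / 14.4% | 6.4 / 9.4 / 10.9% |
| 97% | 5.7 / 8.6 / 11.5% | 4.6 / 5.9 / 8.6% |
| 99% | 1.3 / 2.5 / 3.4% | 1.0 / 1.6 / 2.5% |

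The 90% row agrees with step 1 to within 0.7 percentage points. At ICC 0 no cell exceeds 5.1%. At 99% the exact test is conservative enough to absorb the clustering.

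**Step 3, three arms.** Table 5 has three treatment columns. With 75/75/25 patients the ranges over both mixes and ICC 0.2 to 0.6 are 8.7-18.1% (90% maintenance), 8.0-18.2% (95%), 7.2-17.0% (97%) and 4.0-9.8% (99%). The absence of inflation at 99% is thus a two-arm result.

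**Step 4, alternatives.**

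- *Chi-square or Fisher on the 10.3.5.4 variable, two arms:* size 4.5-5.2% at 90%, 3.8-4.9% at 95%, 1.3-2.7% at 97%, 0.0-0.1% at 99%.
- *Permuting labels across patients on the wound-level proportions* (mix B, 2,000 replicates, 499 permutations): size 3.6-5.6% with two arms, 4.0-5.8% with three.
- *Power for 99% against 95%, two arms, mix B, ICC 0.2 / 0.4 / 0.6:* permutation 42.1 / 37.0 / 30.8%; patient-level test 27.4 / 22.5 / 16.8%. The pooled test shows 38.9 / 40.1 / 40.5%, but without accounting for clustering.
- *Generalised estimating equations:* not estimable, because an arm had no reopened wound, in 47-62% of two-arm and 81-91% of three-arm runs at 99% maintenance.

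**The case against.** **Clustering is ignored elsewhere too.** The analyses that respect it are the primary endpoint, the first secondary endpoint and the non-inferiority safety endpoint. Lower-tier analyses use simple tests on units below the patient: readmissions (11.1.4.15), escharotomy per wound (11.1.5.2), blood loss per procedure (11.1.5.8) and grafting per wound (11.1.5.9). This stands. A reader might infer that maintenance of closure is a lone lapse; the SAP does not support that. The wider practice does not make this p-value valid.

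**The size is assumed.** This also stands. Wound counts, ICC and maintenance rate are all unknown. At ICC 0.1 the two-arm level is only about 5-7%. Closure must be confirmed at two visits two weeks apart (13.1.1), so high maintenance is plausible, although the SAP gives no rate.

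**The consequence is small.** Maintenance is not in the hierarchy of 11.1.8 and is not listed in 7.3.3 or 7.3.4; its derivation sits under an exploratory heading. Patient-level frequencies will be shown, and local target-wound adverse events are tabulated separately. A reader might infer that efficacy or non-inferiority conclusions are at risk; none depends on this test.

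**Arms compared.** A reader might also infer that the SAP leaves the comparison open. It does not in substance. Reference to treatment groups with the three-column Table 5 is the usual wording of 11.1.4, and two-arm comparisons are named where meant, as in 11.1.4.1 and 11.1.4.7.

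**Conclusion.** The point holds as a minor one. The test in 11.1.4.12 uses a unit below the unit of randomisation and makes no allowance for it, although the SAP makes that allowance in its more important wound-level analyses. The error is certain in kind and conditional in size. For 75 against 75 patients with 1 to 3 wounds each and ICC 0.2 to 0.6, the nominal 5% test runs at about 6-15% when 90-95% of wounds stay closed and about 5-12% at 97%. It is not inflated at 99%, hardly inflated at ICC 0.1, and correct if nearly all patients have one target wound. Read as a three-arm test, the inflation is somewhat larger. Only a supporting safety statement about durability of closure is affected.

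**What to change.** In 11.1.4.12, keep the wound-level proportions, both time points and the treatment groups as planned, and replace the source of the p-value. Compute the same chi-square statistic on wound proportions, but refer it to its distribution when treatment labels are permuted across whole patients, so that a patient's wounds stay together. Fix the number of permutations and the seed, as the SAP already does for its imputations. This remains usable when an arm has no reopened wound, where a logistic model gives no usable estimate.

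Permute within randomisation strata where feasible. The factors in 11.1.10 form 2 × 3 × 5 = 30 cells, or 175/30 ≈ 5.8 patients per cell, so a rule for collapsing sparse cells is needed. The figures above are for unrestricted permutation. The safety set groups patients by treatment received, so the permutation argument is exact only where that matches the randomised arm.

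Add the comparison of the 10.3.5.4 variable by chi-square or Fisher as supportive. It should not be the main test: it asks whether all wounds stayed closed, which gives patients with more wounds more chances to fail, and it loses power when reopening is rare.

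**Cost.** A few sentences of SAP text and a little programming; no new data. P-values will generally be less extreme.
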